13.1.3 Target lesions

All measurable lesions up to a maximum of five lesions per organ and 10 lesions in total representative of all involved organs should be identified as **target lesions** and recorded and measured at baseline. Target lesions should be selected on the basis of their size (lesions with the longest diameter) and their suitability for accurate repeated measurements (either by imaging techniques or clinically). A

sum of the longest diameter (LD) for all target lesions will be calculated and reported as the baseline sum LD. The baseline sum LD will be used as reference by which to characterize the objective tumor response.

13.1.4 Non-target lesions

All other lesions (or sites of disease) that are not target lesions as defined in section 13.1.3 will be identified as **non-target lesions** and should also be recorded at baseline. Non-target lesions include measurable lesions that exceed the maximum numbers per organ or total of all involved organs as well as non-measurable lesions. Measurements of these lesions are required when feasible, since a patient may have progressive disease on the basis of larger non-target lesions. The presence or absence of each non-target lesion should be noted throughout follow-up.

13.2 Evaluation of target lesions

Complete Response (CR): Disappearance of all target lesions. The patient must be free of all symptoms of cancer.

Partial Response (PR): At least a 30% decrease in the sum of the longest diameter (LD) of target lesions taking as reference the baseline sum LD. Positive washing, brushing or biopsy and/or residual tumor may still be evident on endoscopy and/or CT scan. No lesion may increase in size and no new lesion may appear.

Progression (PD): At least a 20% increase in the sum of LD of target lesions taking as reference the smallest sum LD recorded since the treatment started or the appearance of one or more new lesions.

Stable Disease (SD): Neither sufficient shrinkage to qualify for PR nor sufficient increase to qualify for PD taking as references the smallest sum LD.

13.3 Evaluation of non-target lesions

Complete Response (CR): Disappearance of all non-target lesions and normalization of tumor marker level.

Non-Complete Response (non CR): Persistence of one or more non-target lesions or/ and maintenance of tumor marker level above the normal limits.

Progression (PD): Appearance of one or more new lesions. Unequivocal progression of existing non-target lesions. (Although a clear progression of "non-target" lesions only is exceptional, in such circumstances, the opinion of the treating physician should prevail, and the progression status should be confirmed at a later time by the reference radiologist (or study chair).

13.4 Evaluation of best overall response

The best overall response is the best response recorded from the start of the treatment until disease progression/recurrence (taking as reference for progressive disease the smallest measurements recorded since the treatment started). The patient's best response assignment will depend on the achievement of both measurement and confirmation criteria.

Target Lesions	Non-target lesions	New lesions	Overall response
CR	CR	No	CR
CR	Non-CR/Non-PD	No	PR
PR	Non-PD	No	PR
SD	Non-PD	No	SD
PD	Any	Yes or No	PD
Any	PD	Yes or No	PD
Any	Any	Yes	PD

1. Patients with a global deterioration of health status requiring discontinuation of treatment without objective evidence of disease progression at that time should be reported as "symptomatic deterioration". Every effort should be made to document the objective progression even after discontinuation of treatment.
2. In some circumstances, it may be difficult to distinguish residual disease from normal tissue. When the evaluation of complete response depends upon this determination, it is recommended that the residual lesion be investigated (fine needle aspirate/biopsy) before confirming the complete response status.

13.5 Guidelines for evaluation of measurable disease

All measurements should be recorded in metric notation using a ruler or calipers. All baseline evaluations should be performed as close as possible to the treatment start and never more than 4 weeks before the beginning of the treatment. The same method of assessment and the same technique should be used to characterize each identified and reported lesion at baseline and during follow-up. Imaging-based evaluation is preferred to evaluation by clinical examination when both methods have been used to assess the antitumor effect of a treatment.

- Clinical lesions will only be considered measurable when they are superficial (e.g. skin nodules, palpable lymph nodes). In the case of skin lesions, documentation by color photography including a ruler to estimate the size of the lesion is recommended.

- Lesions on chest X-ray are acceptable as measurable lesions when they are clearly defined and surrounded by aerated lung. However, CT is preferable.
- Conventional CT and MRI should be performed with cuts of 10 mm or less in slice thickness contiguously. Spiral CT should be performed using a 5 mm contiguous reconstruction algorithm. This applies to the chest, abdomen, and pelvis. Head & neck and extremities usually require specific protocols.
- When the primary endpoint of the study is objective response evaluation, ultrasound (US) should not be used to measure tumor lesions that are clinically not easily accessible. It is a possible alternative to clinical measurements of superficial palpable nodes, subcutaneous lesions, and thyroid nodules. US might also be useful to confirm the complete disappearance of superficial lesions usually assessed by clinical examination.

13.6 Confirmatory measurement/duration of response

Confirmation: The main goal of confirmation of objective response is to avoid overestimating the response rate observed. In cases where confirmation of response is not feasible, it should be made clear when reporting the outcome of such studies that the responses are not confirmed. To be assigned a status of PR or CR changes in tumor measurements must be confirmed by repeat studies that should be performed 4 weeks after the criteria for response are first met. In the case of SD, follow-up measurements must have met the SD criteria at least once after study entry at a minimum interval of 8 weeks.

Duration of overall response: The duration of overall response is measured from the time measurement criteria are met for CR/PR (whichever is first recorded) until the first date that recurrent or progressive disease is objectively documented, taking as reference for progressive disease the smallest measurements recorded since the treatment started).

The duration of overall complete response is measured from the time measurement criteria are first met for CR until the first date that recurrent disease is objectively documented.

Duration of stable disease: Stable disease is measured from the start of the treatment until the criteria for progression are met, taking as reference the smallest measurements recorded since the treatment started.

14.0 CRITERIA FOR REMOVAL FROM STUDY

In the absence of serious toxicity or complications, all patients will receive at least one cycle of treatment. In the absence of treatment delays due to adverse event(s), treatment may continue until one of the following criteria applies:

- Disease recurrence/progression, defined as emergence of an unequivocal new tumor (site of metastasis) > 1 cm in size, clinical progression in non-measurable sites of disease, or unequivocal changes in size of the primary tumor.
- Development of an intercurrent medical condition or need for concomitant treatment that precludes further participation in the trial.
- Unacceptable toxicity or any adverse event that precludes further participation in the trial.
- The investigator removes the patient from the trial in the best interests of the patient.
- Patient death.
- Study completion or discontinuation.
- Patient withdraws consent to continued participation in the trial or is lost to follow-up.

15.0 BIOSTATISTICS

The study is an open-label, non-randomized single-arm, single institution phase I/II therapeutic clinical trial. The study population will be patients with advanced hepatocellular carcinoma.

15.1 Sample size calculation

The phase I component of the study will consist of a traditional 3+3 dose escalation rule with 3 or 6 patients in each cohort, the process for dose escalation is outlined in section 4.1.

The median TTP of patients with advanced HCC treated with sorafenib therapy is 5.5 months. Using this as a benchmark, we will enroll 38 patients, which will allow us to differentiate between a median TTP of 5.5 months and 8.3 months with 80% power and a two-sided significance level of 10% assuming a 24-month accrual and a 12-month follow-up period. TTP will be calculated from initiation of therapy to disease progression (intention to treat) as outlined in section 13.0. Removal from study as outlined in section 14 will be a censored event.

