	
 2. Locally advanced or metastatic disease. 
 a. Patients with locally advanced disease must have disease deemed to be unresectable or not eligible for hepatic transplantation by surgical oncologist or transplant physician 3. Measurable disease, defined as lesions that can accurately be measured in at least one dimension (longest diameter to be measured) according to Response Evaluation Criteria in Solid Tumors (RECIST, version 1.1) at least 2 cm with conventional techniques or at least 1 cm with spiral computed tomography. 4. Child-Pugh Score A or B7. 5. Age \geq 18 years. 6. ECOG Performance Score of 0-2. 7. Absolute neutrophil count \geq 1,200 cells/mm³. 8. Platelet count \geq 70,000 cells/mm³. 9. Total Bilirubin \leq 3.0 mg/dl. 10. Hemoglobin \geq 8.5 g/dl. 11. INR \leq 1.8 (therapeutic anticoagulation allowed as long as medically indicated.) 12. Creatinine \leq 1.5 times upper limit of normal. 13. Women of childbearing potential must have a negative pregnancy test. 14. No clinically significant episode of gastrointestinal bleeding within the previous 30 days. 15. Men and women of childbearing potential must be willing to consent to using effective contraception while on treatment and for at least 3 months thereafter. 16. At least 4 weeks since prior locoregional therapy including surgical resection, radiotherapy, hepatic arterial embolization or chemoembolization, radiofrequency ablation, percutaneous injection or cryoablation (treatment of target lesion only, non-target lesions can be treated with locoregional therapy). Provided the target lesion increased in size by 25% or more or the target lesion
--	---

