3.0 BACKGROUND AND RATIONALE

3.1 Hepatocellular Carcinoma

Hepatocellular carcinoma (HCC) is the fifth most common cancer worldwide and is responsible for more than 500,000 deaths annually. (1) Previously considered uncommon in Western countries, the incidence and mortality of HCC have increased three-fold in the United States over the past two decades. (2) Although complete resection or hepatic transplantation remains the most effective therapies for localized HCC, 50-70% of patients present with advanced disease not amenable to curative surgical approaches. (3,4) Disease that is diagnosed at an advanced stage or with progression after locoregional therapy has a dismal prognosis with a median overall survival of < 12 months mainly due to underlying liver dysfunction and suboptimal treatment options. (2) Ablative therapies are commonly used in this setting but are ineffective for large (>5 cm) or multifocal tumors, both commonly found in advanced disease. (5,6) Hepatic artery chemoembolization may have utility in patients with HCC but there are conflicting reports regarding its efficacy and in advanced disease a survival benefit has not been demonstrated. (7,8)

Systemic Therapy for Advanced Hepatocellular Carcinoma

The use of single agent systemic cytotoxic chemotherapy regimens including

irinotecan, gemcitabine or doxorubicin have historically demonstrated low response rates with little to no clinical efficacy. (9-11) Combination chemotherapy regimens using cytotoxic chemotherapeutic agents have fared no better with response rates ranging from 0% to 40% and limited clinical efficacy. A recent study compared single agent doxorubicin to a combination of cisplatin, interferon, doxorubicin and 5-fluorouracil (PIAF). Despite an improvement in response (10% for doxorubicin vs. 21% for PIAF) the study failed to show an improvement in survival (6.8 vs. 8.6 months, respectively; P=0.83). (12)

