The lack of appropriate traditional chemotherapeutic agents led to the investigation of molecular targeted agents, which have been shown to be efficacious in other tumor models. Sorafenib, an oral multikinase inhibitor that blocks tumor cell proliferation by targeting the Raf/MEK/ERK signaling pathway and exerts an anti-angiogenic effect by targeting the tyrosine kinase receptors, VEGFR-2, VEGFR-3 and PDGF- β , is the first biologically targeted agent to show efficacy in the treatment of advanced stage HCC. (13,14) In a phase III randomized controlled trial (SHARP trial), patients with advanced hepatocellular carcinoma (not eligible for surgical resection or transplantation) and preserved liver function (Child-Pugh A score) were randomly assigned to either systemic sorafenib or placebo. There was a significantly longer survival and radiologic time to progression (TTP) outcome in the cohort of patients that received sorafenib with little or no toxicity. Grade 3 drug related events included diarrhea (8% in the sorafenib group vs. 2% in the placebo group), hand-foot skin reaction (8% vs. 1%), hypertension (2% vs. 1%) and abdominal pain (2% vs. 1%); there were no grade 4 drug-related adverse events in any of these categories in either study group. Currently sorafenib is the only drug that has FDA approval for the systemic treatment of HCC. Although sorafenib is the current standard of care for patients with advanced HCC, it prolonged radiologic time to progression less than 3 months when compared to best supportive care: 5.5 months versus 2.8 months, respectively. Overall survival was prolonged less than 3 months compared to best supportive care, 10.7 months versus 7.9 months, respectively. (14) Although systemic treatment with sorafenib shows statistically significant clinical efficacy, its overall benefit is modest. The complexity of HCC would appear to lend itself to escape mechanisms from the sorafenib-specific blockade of the RAF-MEK-ERK and VEGFR/PDGF pathways, thereby promoting tumor proliferation and neo-angiogenesis through alternative means. Such a mechanism would explain why certain patients fail to benefit from sorafenib therapy and provides the rationale for combining sorafenib with other chemotherapeutic agents.

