Appendix B Child-Pugh Score

Measure	1 point	2 points	3 points
Total bilirubin (mg/dl)	<2.0	2.0-3.0	>3.0
Serum albumin (g/l)	>3.5	2.8-3.5	<3.5
INR	<1.7	1.7-2.2	>2.2
Ascites	None	Mild (based on clinical findings)	Severe (based on clinical findings)
Hepatic Encephalopathy	None	Controlled Medically	Refractory

5-6 points Child-Pugh A
 7-9 points Child-Pugh B
 10-15 points Child-Pugh C

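### Appendix B gives some albumin values two scores and exclusion 17 exists in two conflicting texts; separately, the 5.5-month benchmark comes from Child-Pugh A patients, while the trial enrols A or B7 and plans no Child-Pugh A result

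*Combined protocol and SAP*

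**What the plan says.** **Benchmark.** Section 15.1 states: "The median TTP of patients with advanced HCC treated with sorafenib therapy is 5.5 months". It enrols 38 patients to tell 5.5 from 8.3 months with 80% power at two-sided 10%, with 24 months of accrual and 12 of follow-up. It adds: "Removal from study as outlined in section 14 will be a censored event". The Section 14.0 list of removals includes "Patient death".

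**Source of the benchmark.** Section 3.1 describes the source trial's patients as having "preserved liver function (Child-Pugh A score) were randomly assigned to either systemic sorafenib or placebo". It reports that sorafenib prolonged time to progression "less than 3 months when compared to best supportive care: 5.5 months versus 2.8 months, respectively".

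**Who is enrolled.** The synopsis and Section 6.1 both admit "Child-Pugh Score A or B7". Sections 15.1 and 15.2 plan no Child-Pugh A estimate, adjustment or cap on B7. The only Cox model is for correlative parameters.

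**Albumin row, Appendix B.** Above 3.5 scores 1 point, 2.8 to 3.5 scores 2, and below 3.5 scores 3. The unit printed is g/l. Totals of 5-6 are class A and 7-9 class B, so B7 is the highest eligible total.

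**Exclusion 17.** The synopsis and Section 6.2 both exclude adjuvant sorafenib and other Raf/MEK/RAS or VEGFR inhibitors. Each then adds an exception, and the two exceptions differ.

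**The concern.** In a single-arm trial the fixed benchmark takes the place of the control arm. A difference in case mix between the enrolled patients and the benchmark patients is then read as a drug effect. Here one such difference is visible in the protocol itself: the benchmark is from class A, and the trial takes A or B7. Without a planned class A result a reader cannot see how far the B7 patients move the answer, and a class A result chosen after the data are seen would carry little weight.

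The other two items concern who gets in. If Appendix B gives one patient two totals, sites can enrol or reject the same patient, and any split by class is unreliable. If the two texts of exclusion 17 can be read differently, patients already exposed to adjuvant sorafenib may or may not be compared with 5.5 months. Exclusion 17 bears on prior exposure, not on Child-Pugh class.

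**Working it through.** **1. The plan's own figure.** Assume exponential TTP, uniform entry over 24 months and 12 months' further follow-up. The probability of an observed progression at a median of 8.3 months is O = 0.842. Expected progressions per patient under 5.5 months are E = 0.842 × 8.3/5.5 = 1.270. The one-sample log-rank formula is

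N = [(z.95 × √E + z.80 × √O) / (E − O)]² = [(1.645 × 1.127 + 0.842 × 0.917) / 0.428]² ≈ 37.6,

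which rounds up to 38, with formula power 0.805. The stated sample size reproduces.

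**2. Albumin row.** The eligibility caps (bilirubin 3.0 mg/dl, INR 1.8) limit those two items to 1 or 2 points. Ascites and encephalopathy can score 1 to 3. That gives 2 × 2 × 3 × 3 = 36 patterns of the other four items. For albumin from 2.8 to just under 3.5:

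| Sum of other four items | Patterns | Total if albumin = 2 | Total if albumin = 3 |
|---|---|---|---|
| 4 | 1 | 6 (A) | 7 (B7) |
| 5 | 4 | 7 (B7, eligible) | 8 (ineligible) |
| 6 or more | 31 | 8 or more (ineligible) | 9 or more (ineligible) |

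So all 5 patterns that can be eligible change class or eligibility. These are score patterns, not patient frequencies.

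The unit is a second problem. Since 1 g/dl = 10 g/l, a result of 3.0 g/dl is 30 g/l. Read literally against the printed g/l label it exceeds 3.5 and scores 1 point; entered as 3.0 it scores 2 or 3.

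**3. Exclusion 17, side by side.**

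| | Synopsis, item 17a | Section 6.2, item 17 |
|---|---|---|
| Therapy excepted | adjuvant therapy other than the agents just excluded | prior adjuvant therapy, not limited to other agents |
| Condition | over 6 months, with recurrence or progression | over 6 months, with recurrence |

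The Section 6.2 exception can be read as covering the adjuvant sorafenib excluded in its previous sentence. The synopsis exception cannot.

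**4. Benchmark.** The B7 share and B7 TTP are not in the documents, so both are assumed: 10/20/30% B7 is 4/8/11 of 38. The simulation used 200,000 trials per scenario, exponential TTP, the planned accrual and follow-up, administrative censoring only, and a log-hazard Wald test against 5.5 months at one-sided 5% (the upper half of two-sided 10%). Section 15.1 names no test, so results are compared with the simulated reference of 0.75 power and 0.039 false positives with no B7 patients. A one-sample log-rank simulation gives nearly the same reference, 0.75 and 0.040.

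Power, with the planned ratio 8.3/5.5 applied to everyone:

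| B7 sorafenib-alone median | 10% B7 | 20% B7 | 30% B7 |
|---|---|---|---|
| 5.5 months | 0.75 | 0.75 | 0.75 |
| 5.0 months | 0.73 | 0.71 | 0.70 |
| 4.5 months | 0.72 | 0.67 | 0.64 |
| 4.0 months | 0.69 | 0.63 | 0.57 |
| Class A patients only (34/30/27) | 0.71 | 0.66 | 0.62 |

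False positives, with no added benefit and class A at 5.5 months:

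| B7 sorafenib-alone median | 10% B7 | 20% B7 | 30% B7 |
|---|---|---|---|
| 6.0 months | 0.044 | 0.051 | 0.054 |
| 6.5 months | 0.050 | 0.063 | 0.074 |

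**5. Precision of a class A estimate.** The 90% interval around an observed 8.3 months is 8.3 divided and multiplied by exp(1.645/√events).

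| Patients | Expected events | 90% interval, months |
|---|---|---|
| 38 | 32.0 | 6.2-11.1 |
| 34 | 28.6 | 6.1-11.3 |
| 30 | 25.2 | 6.0-11.5 |
| 27 | 22.7 | 5.9-11.7 |

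**The case against.** The strongest reply is that the benchmark part is a preference. The sample size is arithmetically sound, and a class A result is usually a weaker test than the pooled one: in the power table it wins only when the B7 median is as low as 4.0 months. That stands, and it is why the class A result is offered for interpretation and not as a replacement test.

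Four stronger readings are tempting, and the documents do not support them.

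- **B7 patients progress sooner, so the trial is underpowered.** Section 3.1 ties liver dysfunction to survival ("median overall survival of < 12 months mainly due to underlying liver dysfunction and suboptimal treatment options"), not to TTP. Deaths are among the censored removals. A shorter B7 TTP cannot be presumed.
- **The mismatch seriously inflates false positives.** At a B7 median of 6.0 months the rates are near the nominal 5%. Only the 6.5-month assumption clearly exceeds it, at 20% and 30% B7, and nothing in the documents supports a longer TTP in B7.
- **A class A result makes the comparison fair.** It addresses Child-Pugh class alone. If class A patients here differ from the source trial in other ways, that error remains.
- **Exclusion 17 admits patients given sorafenib earlier for advanced disease.** The item speaks only of adjuvant use. That is a silence; the contradiction lies in the two exceptions.

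On albumin, it can be said that investigators may apply the bands they normally use and ignore the printed ones. That might hide the overlap, but the printed table is the protocol's only definition of the score.

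**Conclusion.** The point holds in three parts of unequal weight.

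- The albumin row is wrong as written. It leaves every potentially eligible score pattern between 2.8 and just under 3.5 with two outcomes, and its unit needs confirming. This rests on no assumption about patients.
- Exclusion 17 is a contradiction between the synopsis and Section 6.2 about whether prior adjuvant sorafenib can be re-admitted. It is a separate matter from the Child-Pugh mix.
- The benchmark mismatch is real, but its direction is unknown and its size depends wholly on assumed B7 shares and medians. Over the range shown, the loss of power runs from nothing to 0.18 (0.75 to 0.57), and the rise in false positives from nothing to 0.035 (0.039 to 0.074). It warrants a cheap addition to the reporting, not a new sample size.

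**What to change.** 1. **Appendix B.** The sponsor reconciles the albumin row, both bands and unit, so that each value has exactly one score.
2. **Exclusion 17.** The sponsor reconciles the synopsis and Section 6.2 into one text and decides which exception applies.
3. **Section 15.1.** Add: *Median TTP with its 90% confidence interval will be reported for all patients and, beside it, for Child-Pugh A patients, the class in which the 5.5-month figure was measured. The number of B7 patients will be given and their TTP described. The all-patient comparison remains primary.* The 90% level matches the two-sided 10% of Section 15.1; the plan at present gives no interval for TTP.

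**Cost.** Two reconciled texts and one table. No new data are needed: Section 8.2 already collects bilirubin, albumin and INR, Child-Pugh class is an eligibility item, and Section 19.0 already requires a Child-Pugh form from satellite sites. The price is the wider class A interval shown above, and the text should not let that estimate be read as a second chance at a positive result.

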2.0 OBJECTIVES AND SCIENTIFIC AIMS

Primary Objectives:

1. The primary objective of the Phase I component of this trial is to determine the maximum tolerated dose (MTD) of bavituximab up to 3.0 mg/kg weekly in patients with hepatocellular carcinoma (not eligible for surgical resection or hepatic transplantation) treated with sorafenib.
2. The primary objective of the Phase II component of this trial is to determine the median radiographic time to progression (from the date of first therapy to date of first documented progression) of patients with hepatocellular carcinoma (not eligible for surgical resection or hepatic transplantation) treated with sorafenib.

Secondary objectives of the trial are to determine the:

3. Safety and tolerability of combination bavituximab and sorafenib treatment in patients with hepatocellular carcinoma.
4. Response rate, progression free-survival and overall survival.
5. Correlation of treatment response with pre- and post-treatment tissue biopsies and serum angiogenic and phosphatidylserine biomarkers.

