Between five and six weeks following the first dose of bavituximab, alpha-fetoprotein(serum), a second image guided core biopsy of an intra-hepatic tumor will be performed.. This second image guided biopsy is optional and will be subject to informed consent with the enrolled patient. This biopsy will be for research purposes only and performed in the exact same way as the clinical care biopsy.

Bavituximab and sorafenib will be administered until intolerable toxicity, or the development of any of the criteria for requiring removal from the study as outlined in Section 14 of the protocol. Serum studies (including alfa-fetoprotein) and CT or MRI will be performed every 6 weeks +/- 5 days following the initial 2-week studies until removal from study. All patients will be followed long-term for the secondary endpoint, overall survival, to a point 12 months from accrual of the final patient.

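### Section 15.1 contradicts itself on the primary endpoint: Section 13 progression is the TTP event, yet every Section 14 removal is censored, and progression heads the Section 14 list

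*Combined protocol and SAP*

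**What the plan says.** Section 2.0 sets the phase II objective as "the median radiographic time to progression (from the date of first therapy to date of first documented progression"). Section 15.1 defines the endpoint in the same spirit: "TTP will be calculated from initiation of therapy to disease progression (intention to treat) as outlined in section 13.0". The next sentence is the only censoring rule the plan gives for it: "Removal from study as outlined in section 14 will be a censored event".

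Section 14.0 opens its list of removal criteria with progression: "Disease recurrence/progression, defined as emergence of an unequivocal new tumor" of more than 1 cm, or "clinical progression in non-measurable sites of disease, or unequivocal changes in size of the primary tumor". Its other criteria are intercurrent illness, toxicity, investigator decision, death, study end, and withdrawal or loss to follow-up.

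Section 13 defines progression differently. Section 13.2 requires a 20% rise in the sum of target-lesion diameters from the smallest sum recorded, or any new lesion. Section 13.3 adds unequivocal progression of non-target lesions, with the treating physician's opinion prevailing if only those have progressed. On what counts as non-target, Section 13.1.4 says: "Non-target lesions include measurable lesions that exceed the maximum numbers per organ or total of all involved organs as well as non-measurable lesions".

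On imaging, Section 4.2.2 says: "CT or MRI will be performed every 6 weeks +/- 5 days following the initial 2-week studies until removal from study". Section 13.4 asks that objective progression be sought even after treatment stops. Section 15.1 does not say whether progression found that way is used.

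**The concern.** The two sentences in Section 15.1 give opposite instructions for the same patient. Someone whose scan shows a new 2 cm lesion has progressed under Section 13 and also meets the first removal criterion of Section 14. The first sentence makes that an event and the second makes the removal a censoring. No passage says which prevails.

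The trial has no control arm, and its result is read against a fixed 5.5 months. Censoring progressions lengthens the estimated median and moves the result towards the 8.3-month target. A choice between the two readings made after the data are seen would be post hoc, on the primary endpoint.

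There is a second, smaller issue. Because Section 14 words progression more loosely in places than Section 13, some patients could be removed for worsening disease without a Section 13 event. They would be censored just as they worsen, and their scheduled scans would stop.

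**Working it through.** **1. Does the design count progressions as events?** Inputs from Section 15.1: medians 5.5 and 8.3 months, 38 patients, 80% power, two-sided 10% level, 24-month accrual, 12-month follow-up. Assumptions: exponential TTP, uniform accrual.

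- Hazards: ln 2/5.5 = 0.1260 and ln 2/8.3 = 0.0835 per month.
- Chance that a progression is observed: 1 − (e^(−12λ) − e^(−36λ))/(24λ).
 - At 5.5 months: 1 − (0.2204 − 0.0107)/3.0246 = 0.931.
 - At 8.3 months: 1 − (0.3671 − 0.0495)/2.0043 = 0.842.
- Expected events: 38 × 0.931 = 35.4 and 38 × 0.842 = 32.0.
- Sample size on the median scale: [(1.645 × 5.5/√0.931 + 0.842 × 8.3/√0.842)/(8.3 − 5.5)]² = 36.8, so 37. A one-sample log-rank test with null variance gives 37.8, so 38, and simulated power at 38 is 80.0%.

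The plan names no formula, and other variants give 40 to 47. But 38 reproduces when all progressions count, so the design relies on them.

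**2. The censoring sentence applied as written (worst case).** Let g be the share of progressions censored at the progression date, independent of time. The counted hazard becomes (1 − g)λ, so the apparent median is 5.5/(1 − g) when the true median is 5.5. Expected events are 35.4 × (1 − g).

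| g (assumed) | Apparent median, months | Expected events | Trials with median not reached |
|---|---|---|---|
| 25% | 7.3 | 26.5 | 0% |
| 50% | 11.0 | 17.7 | 2% |
| 75% | 22 | 8.8 | 45% |
| 90% | 55 | 3.5 | 86% |

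The 8.3-month target is reached at g = 1 − 5.5/8.3 = 0.337. The last median lies beyond the maximum follow-up of 24 + 12 = 36 months. Even on this reading g is not 100%: a new lesion of 1 cm or less, or growth confined to target lesions other than the primary tumor, meets Section 13 without meeting Section 14.

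**3. The two progression definitions side by side.**

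| Section 14 wording | Also a Section 13 event? |
|---|---|
| New tumor over 1 cm | Yes; 13.2 counts any new lesion |
| Clinical progression at non-measurable sites | Yes if unequivocal (13.1.4, 13.3); otherwise no |
| Unequivocal change in primary tumor size | Only if the 20% rise in 13.2 is reached |

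Only the parts of the second and third rows that fall short of Section 13 remain, so the group is probably small.

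**4. The likely intended reading.** Section 13 progression always counts, but a share f of progressions is preceded by a Section 14-only removal and censored then. Further assumptions: true median 5.5, one-sample log-rank Z = (O − E)/√E, rejection below −1.645 (a 5% tail; the plan names no test), removal 6 weeks (1.38 months) before Section 13 progression.

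| f (assumed) | Patients of 38 | Apparent median, months | False positives |
|---|---|---|---|
| 0% | 0 | 5.5 | about 4% |
| 2% | about 1 | 5.6 | about 5% |
| 5% | about 2 | 5.7 | 6.5 to 7% |
| 10% | about 4 | 6.0 | about 11% |

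With removal 12 weeks before, f of 5% and 10% give medians of 5.7 and 5.9 months and false positives of 6.4% and 9.9%.

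**The case against.** The strongest reply is that the text can be read without contradiction. Section 15.1 first makes Section 13 progression the event, and Section 2.0 dates it at first documentation. A patient removed because of documented progression has already had the event by the removal date. Censoring after an event has no effect, and at tied times events are conventionally taken first. On that reading the censoring sentence reaches only removals without prior Section 13 progression.

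This is probably what was meant, and it rules out the stronger inference a reader might draw: that progressions will drop out of the analysis and the median will be badly inflated or not reached. The documents do not support that as a prediction. They do not give g, and a median that is often not reached needs g well above one half. What the reply does not do is supply the missing rule. The sentence names Section 14 as a whole, progression is part of Section 14, and the analyst has to bring in the order of precedence.

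It is also fair to say that the remaining bias may be negligible. At f of 1 to 2% false positives are 4.4 to 5.1%, close to the nominal 5%. Sections 13.2 and 13.3 already capture most of the Section 14 wording, and Section 13.4 asks for later progression to be documented. If the benchmark trial censored such patients in the same way, the comparison is affected less still; the documents do not say. All of this stands, and it is why the remaining issue is described as probably small.

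**Conclusion.** The contradiction is real and sits in the only censoring rule for the phase II primary endpoint, so it should be removed before analysis. That conclusion rests on the text, not on any assumed share.

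The size depends on the reading. As written, the apparent median for a regimen with no benefit is 5.5/(1 − g), which equals 8.3 months at g of about 34%; this is a worst case on a reading that is probably not intended. On the likely reading, false positives rise from about 4% to about 5%, 6.5 to 7% and 11% at assumed f of 2%, 5% and 10%. These figures assume exponential times, the stated lag and a one-sample log-rank test.

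Two further inferences are not supported. The sample size of 38 is not wrong on this account, since it reproduces with progressions counted. Nor is any bias shown from censoring removals for toxicity, death, withdrawal or loss to follow-up; censoring deaths without progression is a usual convention for TTP.

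**What to change.** Replace the censoring sentence in Section 15.1 with wording such as: *The TTP event is first progression by Section 13, on the date first documented, whether or not it also leads to removal under Section 14. Section 13 progression documented after removal is used. Patients without Section 13 progression are censored at their last adequate tumor assessment.*

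Reconcile the progression wording of Sections 13 and 14. Which removal wording is right is for the investigators and is not decided here.

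Report one sensitivity analysis that counts removals for Section 14-only progression as events at the removal date. The rewording settles the contradiction but hardly changes the residual bias: at f = 10% with a 6-week lag and no scans after removal, the median moves from 6.02 to 5.96 months. The sensitivity analysis bounds that bias from the other side and can err low: 5.44 and 5.37 months at f of 5% and 10% when the truth is 5.5. It belongs beside the primary result, not in its place.

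The cost is a few sentences and a little analysis work. Identifying the relevant removals needs their reasons. The withdrawal list in Section 15.2 has no category for clinical progression beyond lack of efficacy, so the reasons would come from source notes or, optionally, one added field. The sensitivity result may look less favourable. The sample size stays at 38.
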